15.6 Interim Analysis

Comprehensive safety interim reports will be provided twice yearly to the DSMB, along with abbreviated quarterly reports. Quarterly reports will include SAE tabulations by treatment group. Comprehensive, twice yearly safety reports will include detailed summaries of all SAEs, AEs, laboratory parameter listings, drug discontinuations and withdrawals as well as other pertinent safety data. The DSMB will recommend continuation or discontinuation of the study based on these interim reviews. Any interim analyses with respect to efficacy or futility will be outlined in the DSMB charter.

Version 2.0 Version Date: 28 AUG 14 Page 42 of 57

15.7 Sample Size and Randomization

The primary endpoint is the difference between treatment groups in the proportion of subjects with a 5% or greater improvement in the relative change in FEV₁ in liters from baseline to Day 28. A 5% or greater improvement in the relative change is well established as a minimum clinically important change by CF physicians based on the choice of the non-inferiority margin of 4% in a recent Phase 3 clinical trial (46) and the effect size of a number of key therapies utilized in CF (43:47-52). A responder-based endpoint is also an established approach for identifying efficacy on an individual patient level, as opposed to highly variable average changes across patients within a treatment group. In the recently completed pilot study of gallium, 8 of 11 (73%) experienced a 5% or greater relative change in FEV₁ from baseline to Day 14 and 5 of 11 (45%) experienced a 5% or greater relative change in FEV₁ from baseline to Day 28. There was no placebo group in the study; however, data from a completed randomized trial of azithromycin in subjects chronically infected with P. aeruginosa was used to estimate the expected responder rate among those receiving placebo (43). In this study, the proportion of placebo subjects with a 5% or greater relative improvement in FEV₁ ranged from 28% to 33% across study visits from Day 28 through Day 84. Thus, the expected treatment difference in this study is between approximately 15% and 45% based on the observed response rates from the gallium pilot study. However, it is felt that the minimum clinically important difference between groups is based on clinician opinion is 30% given the treatment burden of an intravenous therapy (e.g., increasing the responder rate from 30% to 60%). With a sample size of 60 per group and assuming a responder rate of 30% in the placebo group, the study has 90% power to detect a 28.3% or greater improvement in the responder rate. Accounting for an attrition rate of 10% and interim analyses, the study will still have 90% power to detect a treatment difference of 30.0% or greater between groups.

A key secondary endpoint is the difference between treatment groups in the average relative change in FEV₁ from baseline (Day 1) to Day 28. Based on estimates from prior CF clinical trials among CF patients chronically infected with *P. aeruginosa*, the expected standard deviation of the relative change over a 28 day period ranges from 9 – 23 (43;53). A two-sided .05 level two-sample t-test will be used to test for differences between treatment groups with respect to the 28 day relative change. With a sample size of 60 per group and a standard deviation as low as 9 or as high as 23, the study would have 90% power to detect a minimum of 5.4% or 13.7% difference in the 28 day relative change between treatment groups, respectively. Additionally, the study has 90% power to detect a 0.78 log difference between treatment groups with respect to change in bacterial density assuming a standard deviation of 1.3 based on prior studies in CF(43).

Study personnel at the investigative site will use the Medidata Rave[®] and BalanceTM systems to randomize each subject. Medidata BalanceTM is a dynamic randomization and trial supply management solution that is fully unified with the Rave[®] EDC system. An adaptive randomization (dynamic allocation based on minimization) (54) will be employed with the goal of ensuring equal representation in each study arm based on lung function (FEV₁). Subjects will be randomly assigned in a 1:1 ratio to one of two arms: (1) IV placebo infusion, or (2) IV gallium nitrate solution. Subject randomization will be stratified by baseline FEV₁ group (FEV₁ < 50% of predicted, 50-70% of predicted and >70% of predicted). The dynamic allocation algorithm seeks to optimize randomization balance by minimizing a weighted average of the marginal imbalance of treatment allocation for each factor and for the study overall (55). A

Version 2.0 Version Date: 28 AUG 14 Page 43 of 57

random element is added to the otherwise deterministic minimization algorithm to reduce allocation predictability by using a biased coin (56) to include a chance of allocation to a treatment arm other than the arm that optimizes balance. Access to the randomization code will be strictly controlled and limited to select members of the Biostatistics and Clinical Data Management unit at the TDNCC and the central pharmacy.

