8 STUDY TREATMENTS

8.1 Method of Assigning Subjects to Treatment Groups

Approximately 120 eligible subjects will be randomly assigned to receive study drug (IV gallium or placebo) in equal allocation. An adaptive randomization will be employed with the goal of ensuring equal representation in each study arm as noted in the Statistical Analysis Plan (SAP). Subject randomization will be stratified by baseline FEV_1 group ($FEV_1 < 50\%$ of predicted, 50-70% of predicted and >70% of predicted). Randomization will occur centrally using a web based randomization system linked to the electronic data capture (EDC) system. Only authorized site personnel are given access to the randomization module. Authorized site

Version 2.0 Version Date: 28 AUG 14 Page 24 of 57

personnel will enter subject eligibility information and whether or not the subject signed informed consent. The system will verify that the subject is eligible and has provided signed informed consent, and then provide the appropriate authorized site personnel with a randomization assignment for that subject that matches a specific treatment.

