15 STATISTICAL METHODS AND CONSIDERATIONS

Prior to the analysis of the final study data, a detailed SAP will be written describing all analyses that will be performed. The SAP will contain any modifications to the analysis plan described below. Except where otherwise noted, all tests will be two-sided and statistical significance will be determined at the 0.05 level.

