15.3 Analysis of Primary Endpoint

The primary endpoint is the difference between treatment groups in the proportion of subjects with a 5% or greater relative change from baseline to Day 28 of FEV₁ measured in liters, calculated as:

$$\frac{(Day\ 28\ FEV_1-Day\ 1\ FEV_1)*100}{Day\ 1\ FEV_1}$$

To test the null hypothesis that there is no difference between the treatment groups, a two-sample test of proportions will be performed adjusted for baseline FEV₁ strata. The difference between treatment groups will be provided with associated 95% CI. Additional analyses of the relative change in FEV₁ through Day 56 will include the development of a mixed-effect model for repeated measures (MMRM). Adjusted means and 95% CIs will be presented for each visit. Treatment comparisons of the average response at each visit will be generated within the MMRM model based on the linear contrast of the average using the estimated least square means (LSMeans) at Days 14, 28, and 56.

Missing data methods will be described in the SAP.

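### Optional, nearly free improvement: section 15.7 tests the key secondary endpoint (Day 28 relative change in FEV₁) with an unadjusted t-test, although allocation is balanced on baseline FEV₁ strata and the primary test is adjusted for them

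*Protocol*

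**What the plan says.** Protocol section 15.7 defines the endpoint: "A key secondary endpoint is the difference between treatment groups in the average relative change in FEV₁ from baseline (Day 1) to Day 28". It then names the test: "A two-sided .05 level two-sample t-test will be used to test for differences between treatment groups with respect to the 28 day relative change". No stratum or covariate is mentioned.

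Allocation uses baseline lung function. Section 8.1 says "Subject randomization will be stratified by baseline" FEV₁ group (below 50%, 50–70% and above 70% of predicted). Section 15.7 describes the algorithm as "minimizing a weighted average of the marginal imbalance of treatment allocation for each factor and for the study overall", with a biased coin added.

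The primary endpoint is the responder version of the same Day 28 variable. For it, section 15.3 says "a two-sample test of proportions will be performed adjusted for baseline" FEV₁ strata.

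Section 15.3 also plans a mixed model for repeated measures (MMRM) of relative change in FEV₁ through Day 56, described as an additional analysis. Of this model it says "Adjusted means and 95% CIs will be presented for each visit", and it promises treatment comparisons visit by visit, "based on the linear contrast of the average using the estimated least square means (LSMeans) at Days 14, 28, and 56". It does not say what the means are adjusted for.

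Section 15 adds: "The SAP will contain any modifications to the analysis plan described below".

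**The concern.** Day 28 relative change in FEV₁ is analysed in two forms. The dichotomised form is adjusted for the strata used in allocation. The continuous form, in the sentence that names its test, is not, and the protocol gives no reason for the difference.

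Balancing the arms on a prognostic factor removes most of that factor's contribution to the difference between arms. A t-test that ignores the factor still counts the between-stratum variance in its standard error. The interval is then wider than it need be, and the true type I error falls below the nominal 5%. What is at stake is some precision on a key secondary endpoint, not its validity.

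The protocol also does not say whether the t-test or the MMRM decides this endpoint.

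**Working it through.** **Inputs from section 15.7.** 60 per arm, 1:1 allocation, two-sided 0.05, SD of relative change 9 to 23, detectable differences 5.4 (SD 9) and 13.7 (SD 23) at 90% power.

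**Assumption.** R² is the share of outcome variance explained by the three strata. The protocol gives no value, so 0, 0.05, 0.10 and 0.20 are used.

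**1. Reproduce the stated figures.** The standard error of the difference is SD × √(2/60): 9 × 0.1826 = 1.643 and 23 × 0.1826 = 4.199. With the noncentral t on 118 degrees of freedom, the difference detectable with 90% power is 5.370 (SD 9) and 13.724 (SD 23). Power is 90.3% at 5.4 and 89.9% at 13.7. The stated figures reproduce.

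**2. The t-test when strata are balanced.** The t-test uses SD × √(2/60), but the true standard error is smaller by the factor √(1 − R²). Hence:
- excess interval width = 1/√(1 − R²) − 1
- type I error ≈ 2 × [1 − Φ(1.96/√(1 − R²))]
- power at 5.4 (SD 9) ≈ Φ[(5.4/1.643 − 1.98)/√(1 − R²)] = Φ[1.306/√(1 − R²)]

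**3. The stratum-adjusted linear model.** Residual SD = SD × √(1 − R²), noncentral t on 116 degrees of freedom.

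| Assumed R² | 0 | 0.05 | 0.10 | 0.20 |
|---|---|---|---|---|
| t-test interval too wide by | 0% | 2.6% | 5.4% | 11.8% |
| t-test type I error | 5.0% | 4.4% | 3.9% | 2.8% |
| t-test power at 5.4, SD 9 | 90.4% | 91.0% | 91.6% | 92.8% |
| Adjusted power at 5.4, SD 9 | 90.3% | 91.7% | 93.0% | 95.4% |
| Net gain, points | about 0 | 0.7 | 1.4 | 2.6 |
| Adjusted half-width of 95% CI, SD 9 (t-test 3.25) | 3.25 | 3.17 | 3.09 | 2.91 |
| Adjusted half-width of 95% CI, SD 23 (t-test 8.32) | 8.32 | 8.11 | 7.89 | 7.44 |

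The 90.4% against 90.3% at R² = 0 comes from the normal approximation in step 2. On the exact noncentral t, the loss from two extra degrees of freedom is about 0.01 point (90.31% to 90.30%), and the detectable difference moves from 5.370 to 5.371.

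**4. Check by simulation.** 20,000 trials of 120 patients were simulated per setting, with minimisation on three equal strata and a biased coin of 0.8 (shares and coin are assumptions). For R² of 0, 0.05, 0.10 and 0.20, t-test type I error was 5.0%, 4.6%, 3.9% and 3.1%; the adjusted test stayed between 4.9% and 5.3%. Power at 5.4 (SD 9) was 90.4%, 91.0%, 91.2% and 92.3% for the t-test, and 90.4%, 91.8%, 92.9% and 95.2% adjusted. The pattern agrees with the table without assuming exact balance.

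**The case against.** The strongest reply is that nothing here is an error. The t-test is valid and at worst conservative. Its sentence sits in the sample-size section, between the SD assumption and the detectable differences, where it may have been meant mainly as the basis for power. The SAP may modify the plan. All of that stands, and it is why the point is optional. But the sentence prescribes how the groups will be compared, and a test the protocol has named holds unless the SAP changes it.

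A second reply is that the MMRM already covers the endpoint. A reader might infer from the phrase about a contrast of the average that the MMRM offers no Day 28 comparison. The document does not support that: the same sentence promises comparisons visit by visit and lists Day 28, so a Day 28 contrast is a fair reading. What remains is that the MMRM is called additional, its covariates are not stated, and its rank against the t-test is not given.

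A third reply is that the gain is assumed. This stands too. No R² is given, relative change is already divided by baseline, and nothing in the protocol supports the upper end of the range. The calculations also take 60 observed per arm, while section 15.7 expects 10% attrition. With 54 per arm, the t-test's nominal power at 5.4 (SD 9) is 87.1%.

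**Conclusion.** The point holds as an optional improvement. Section 15.7 names an unadjusted test for an endpoint whose allocation strata are known and are already used for the primary test. With 60 observed per arm and assumed R² of 0, 0.05 and 0.10, the t-test interval is about 0%, 3% and 5% too wide. Adjusting gains about 0, 0.7 and 1.4 points of power net, and 2.6 points at R² = 0.20. The true gain may be near zero.

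Three stronger readings are not supported. The t-test does not inflate the type I error; any departure is downwards. The stated power is not wrong; 5.4% and 13.7% reproduce. And the protocol gives no ground for ranking a single-visit linear model above the MMRM: with 10% attrition expected, the MMRM can use the other visits of patients who lack a Day 28 value, so the choice between the two is open.

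**What to change.** In section 15.7, keep the t-test as the basis of the power calculation only, and name one deciding analysis adjusted for stratum. For example:

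> The power calculation for this endpoint is based on a two-sided .05 level two-sample t-test. The treatment difference in relative change in FEV₁ at Day 28 will be tested at the two-sided .05 level in [one of the following], adjusted for baseline FEV₁ stratum (<50%, 50–70%, >70% of predicted).

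The bracket should hold one choice: a linear model with treatment and stratum, or the Day 28 treatment contrast of the MMRM in section 15.3 with stratum as a covariate. If the MMRM is chosen, section 15.3 should state that contrast and covariate explicitly.

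The cost is wording. In the linear model it takes two of 118 degrees of freedom, about 0.01 point of power if the strata predict nothing. No new data are needed, since the stratum is known at randomization. The sample size and the 5.4% and 13.7% figures stay as they are.

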6.2 Inclusion Criteria

- 1. Greater than or equal to 18 years of age at Screening
- 2. Documented chronic colonization with *P. aeruginosa* defined as identification in two sputum or oropharyngeal cultures within the year prior to Day 1
- 3. Documentation of a CF diagnosis as evidenced by one or more clinical features consistent with the CF phenotype **and** one or more of the following criteria:
 - a. sweat chloride \geq 60 mEq/liter by quantitative pilocarpine iontophoresis test (QPIT)
 - b. two well-characterized mutations in the cystic fibrosis transmembrane conductance regulator (CFTR) gene
 - c. Abnormal nasal potential difference (NPD; change in NPD in response to a low chloride solution and isoproteronol of less than -5 mV)
- 4. $FEV_1 \ge 25$ % of predicted value at Screening
- 5. Able to expectorate sputum
- 6. Serum liver function tests ≤ 2.5 x upper limit of normal at Screening
- 7. Serum urea nitrogen (BUN) ≤ 1.5 x upper limit of normal at Screening
- 8. Serum creatinine $\leq 2.0 \text{ mg/dl}$ and $\leq 1.5 \text{ x upper limit of normal at Screening}$
- 9. Hemoglobin \geq 9 g/dl, platelets \geq 100,000/mm³, and white blood cells (WBC) \geq 4,500/mm³ at Screening
- 10. Ionized calcium ≥ lower limit of normal at Screening
- 11. Written informed consent obtained from subject or subject's legal representative, able to communicate with the Investigator and comply with the requirements of the protocol
- 12. If female and of childbearing potential, must have a negative pregnancy test on Day 1 prior to receiving study drug
- 13. If female and of childbearing potential, is willing to use adequate contraception for the duration of the study through Visit 5, as determined by the investigator
- 14. If male and able to father a child, is willing to use adequate contraception for the duration of the study through Visit 5, as determined by the investigator
- 15. Clinically stable with no significant changes in health status within 14 days prior to Day 1

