15.4 Analysis of Secondary Endpoints

Summary statistics (mean, standard deviation, median and range) of lung function parameters, sputum density, CFRSD-CRISS, and blood inflammatory markers for each visit and changes from baseline will be presented by treatment group. Descriptive statistics will be used to summarize the proportion of subjects initiating acute antibiotics (by route) and differences in proportions between the study arms will be estimated with accompanying 95% CIs.

Changes in lung function parameters (FVC in liters, FVC % predicted and FEV₁ % predicted), sputum bacterial density, CFRSD-CRISS, and inflammatory markers will be analyzed using MMRM. Adjusted means and 95% CIs will be presented for each visit. Treatment comparisons of the average response at each visit will be generated within the MMRM model based on the linear contrast of the average using the estimated LSMeans at Days 14, 28, and 56.

A log transformation will be used in all analyses of quantitative sputum culture counts and blood inflammatory markers. Change in bacterial density will include only those subjects with the pathogen at baseline. Additional descriptive analyses will be performed to summarize the disappearance and emergence of the pathogens and their susceptibility to gallium.

Version 2.0 Version Date: 28 AUG 14 Page 41 of 57

For those subjects randomized to receive IV gallium, we will determine of the Css and $t_{1/2\beta}$ by analyzing Days 1, 6, 14, 28 and 56. Clearance will be determined as the ratio of the infusion rate to the steady state concentration immediately prior to completion of the infusion. The $t_{1/2\beta}$ will be determined as 0.693/K where K is the elimination rate constant determined by the slope of the concentration/time curve after the infusion has been discontinued. To avoid unblinding, samples will only be assayed at the end of the completion of the trial.

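### The 90% power claimed for a 0.78 log difference in P. aeruginosa density needs all 60 subjects per arm analysed, which the protocol's own attrition and baseline-positive rule rule out

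*Protocol*

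**What the plan says.** All of this is in the protocol.

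- **Power claim (section 15.7).** "Additionally, the study has 90% power to detect a 0.78 log difference between treatment groups with respect to change in bacterial density". The SD behind it is 1.3, taken from earlier CF studies. This sentence gives no sample size of its own. It follows one on FEV₁ that begins "With a sample size of 60 per group and a standard deviation as low as 9 or as high as 23".
- **Attrition (section 15.7).** For the responder endpoint the detectable difference is widened from 28.3% to 30.0%: "Accounting for an attrition rate of 10% and interim analyses, the study will still have 90% power". The density figure gets no such allowance. Section 12.3 rules out replacing subjects who stop drug or withdraw.
- **Analysis set (section 15.4).** "Change in bacterial density will include only those subjects with the pathogen at baseline".
- **Eligibility (section 6.2, inclusion 2).** Chronic colonization is "defined as identification in two sputum or oropharyngeal cultures within the year prior to Day 1".
- **Timing of the baseline culture.** The microbiology footnote in Appendix 1 allows no culture at a separate screening visit, so the only pre-dose study culture is the Day 1 sputum. Under section 9.4.1 it is shipped overnight to a central laboratory and processed within two days. Sections 10.1.1 and 10.1.2 place randomization and the start of infusion on Day 1. Eligibility is to be confirmed once laboratory results arrive, but this culture is not an eligibility criterion.

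**The concern.** The power sentence counts everyone randomized, whereas the analysis rule counts only those positive at baseline who also have follow-up. A subject can qualify on two cultures from the past year (possibly oropharyngeal), be randomized and dosed, turn out to have no P. aeruginosa in the Day 1 sputum, and so leave this analysis. The rule in section 15.4 foresees such subjects; the power figure allows for none. Ordinary attrition, which the same section puts at 10%, is also left out.

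Reducing P. aeruginosa is a named secondary objective and the direct readout of the proposed antimicrobial mechanism. Section 1.2 reports no significant change in quantitative culture and wide variability in the phase 1b study, so a null result is plausible. With the present sentence in the protocol, a reader could take such a result as evidence against a 0.78 log effect from a comparison with 90% power, when the power is lower.

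**Working it through.** **Inputs**

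- Two-sided α = 0.05 (section 15: "all tests will be two-sided and statistical significance will be determined at the 0.05 level").
- SD = 1.3 log and difference d = 0.78 log (section 15.7; the log base is not stated).
- 60 randomized per arm, 1:1 (section 15.7).
- Attrition 10% (section 15.7, stated for the primary endpoint).
- Share positive at baseline: not in the protocol. 95%, 90%, 80% and 70% are assumptions chosen to show a range.

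**Method.** Two-sample t-test with n analysed per arm:

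δ = d / (SD × √(2/n)), power = P(T > t₀.₉₇₅,₂ₙ₋₂), where T is noncentral t with 2n − 2 degrees of freedom and noncentrality δ. The detectable difference is the d at which this power equals 0.90.

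**Step 1: reproduce the plan's figure.** With n = 60, SD × √(2/n) = 1.3 × √(2/60) = 0.2373, so δ = 0.78 / 0.2373 = 3.286. The critical value is 1.980 on 118 df. Power is 90.3% and the detectable difference is 0.776, which rounds to 0.78. The stated figure is therefore correct for 60 analysed per arm.

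**Step 2: the margin.** Solving for n at d = 0.78 and 90% power gives 59.4, so 60 per arm. At 59, power is 89.8%. There is nothing in reserve for losses.

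**Step 3: the protocol's own attrition.** 60 × 0.90 = 54 per arm. SD × √(2/54) = 0.2502 and δ = 0.78 / 0.2502 = 3.118. Power is 87.1% and the detectable difference 0.818 log. This step needs no outside figure.

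**Step 4: add the baseline-positive restriction.** n = 54 × assumed share, rounded to whole subjects.

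| Assumed share positive at Day 1 | n per arm | Power at 0.78 log | Difference at 90% power |
|---|---|---|---|
| 100% | 54 | 87.1% | 0.82 |
| 95% | 51 | 85.1% | 0.84 |
| 90% | 49 | 83.6% | 0.86 |
| 80% | 43 | 78.5% | 0.92 |
| 70% | 38 | 73.3% | 0.98 |

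The first row rests on protocol figures plus the most favourable possible share; the others rest on the assumed shares. The table treats attrition and baseline positivity as independent.

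**The case against.** The strongest reply is that section 15.7 contains no arithmetic error. The figure is right for 60 per arm, and the FEV₁ detectable differences just before it also use the full 60, so quoting power at the nominal size looks like the paragraph's convention. This is true, but it does not help: the fault is that 60 is not the size of the analysis set defined in section 15.4. The FEV₁ figures share the attrition omission (at 54 per arm, 5.4% becomes about 5.7% and 13.7% about 14.5%); they do not justify it.

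Second, the loss from baseline-negative subjects may be small. Subjects must be able to expectorate and must have two positive cultures, which may be recent. They must also have been off inhaled antibiotics for 7 days and off acute antibiotics for 14 days. This stands as a reason to treat the 70% to 80% rows as illustrative and not as expected.

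Third, the planned analysis is an MMRM, not a t-test. Sputum cultures are scheduled at Days 28 and 56. If the contrast averaged the two changes, the effect persisted to Day 56 and the changes correlated at 0.8, the SD would shrink by √((1 + 0.8)/2) = 0.949, and 0.818 × 0.949 = 0.776 would cancel the attrition loss. The protocol supports none of these values, and the model cannot recover subjects excluded as baseline-negative.

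Finally, section 15.4 requires 95% confidence intervals, and these show what a null result excludes, whatever the planning sentence says. That limits the harm but does not make the sentence correct.

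**Conclusion.** The concern holds. The claimed 90% power at 0.78 log requires 60 analysed per arm, and the protocol's attrition allowance, its no-replacement rule and its baseline-positive analysis set together mean fewer will be analysed.

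On the protocol's own 10% attrition, and with every subject positive at Day 1, power at 0.78 log is 87% and the difference detectable with 90% power is 0.82 log. Any baseline-negative subjects lower the power further, by an amount that depends on a share the protocol does not give. These figures assume the stated SD of 1.3 and a two-sample t-test.

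The consequence is modest. This is a secondary endpoint, the figure does not set the sample size, and the documented shortfall is about 3 percentage points of power (90.3% to 87.1%). The sentence should be corrected, but the design need not change.

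**What to change.** In section 15.7, replace the density power sentence with one for the subjects who will be analysed. State the expected analysable number per arm after 10% attrition and after removing baseline-negative subjects, the assumed share positive at Day 1 with its basis, and the resulting detectable difference. That is 0.82 log at 90% power with 54 per arm if all are positive; at an assumed 80% positive (43 per arm) it would be 0.92 log. If the sponsor prefers to rely on the MMRM for precision, the assumed correlation and visit contrast should be stated too. The FEV₁ sentence just before it could be put on the same post-attrition basis.

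The cost is one sentence and a slightly less favourable detectable difference. No patients, visits or procedures are added.
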